**c) Number of Subjects**

Up to 100 subjects will be enrolled initially. The research plan will be to have at least 40 evaluable subjects [half receiving true stimulation and half sham stimulation during the blinded phase of the study]. Thus we are allowing for up to 60 subjects who may be screen failures or drop outs for any reason.

**d) Study Timelines**

	Protocol Name:	Vagus Nerve Stimulation: A Non-Invasive Treatment to Improve the health of Gulf Veterans with Gulf War Illness
	Principal Investigator:	[name]
	Primary Contact Name/Contact Info:	[name]: [contact]
	Date Revised:	07/15/2019
	Study Number:	HSM# 16-00097

The VA part of the study will take up to 2 weeks. The ISMMS part of the study will consist of two parts – the blinded phase of the study which will be 10 weeks in duration and which will be followed by the open label phase of the study for an additional 10 weeks.

Allowing for scheduling, an individual will be in the study for up to 24 weeks.

The study is funded for three years. We expect to complete enrollment and data collection by the third quarter of the third year. We expect to have results in the final quarter of that year and will use them to prepare a proposal for funding a multi-site follow up trial to provide data to obtain FDA approval for use the device in treating the widespread pain of GWI.

### e) Endpoints

**Primary:** To assess the effectiveness of the active treatment compared with the sham treatment groups in reducing widespread pain severity occurring in the past 24 hours as measured by five assessments using a VAS one week prior to study enrollment and one week prior to termination of the blinded phase of the trial. Assessment of this objective will be based on differences between active vs sham treatment data as well as between baseline and end of treatment data.

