### 1) Objectives

**Research Question:** The major research question is to determine if VNS reduces the widespread pain of GWI while sham VNS does not. Next, for those veterans with comorbid migraine, the question is to determine if number and severity of migraine headaches are lessened by VNS in contrast to sham VNS.

**Specific Aims:** (1) To conduct a small randomized clinical trial ( $n \leq 44$ ) to evaluate the efficacy of self-administered, non-invasive, active nVNS in veterans with GWI as compared to sham treatment. (2) To provide clinical proof-of-principle data and support future development of broader efficacy studies for GWI

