	Protocol Name:	Vagus Nerve Stimulation: A Non-Invasive Treatment to Improve the health of Gulf Veterans with Gulf War Illness
	Principal Investigator:	[name]
	Primary Contact Name/Contact Info:	[name]: [contact]
	Date Revised:	07/15/2019
	Study Number:	HSM# 16-00097

*Statistical approach to data:* Safety data will be derived from every subject who used either sham or non-sham apparatus for any period of time. Therapeutic efficacy will be evaluated using both intent-to-treat (for all subjects who sign consent with those dropping out recorded as showing no change from baseline) and per protocol (for subjects who completed the 10 weeks of the blinded phase of the trial).

*Blinded study:* Our primary outcome variable will be post-intervention pain severity in the treatment versus sham condition, controlling for pain severity prior to randomization. We will define success for this variable if it decreases by 30% or more over the course of the trial. Five days of VAS data on pain severity will have been collected prior to randomization and during the last week of the 2.5-month stimulation period. For the primary analysis, these will be averaged to create a single pre-intervention and a single post-intervention pain severity score for each person. Post-intervention pain severity will be regressed on pre-intervention pain severity and intervention condition, using an analysis of covariance (ANCOVA) procedure.

A second analysis will use the pre and post measures of pain severity described above, along with pain severity assessments collected a third of the way and two thirds of the way through the 10 week blinded phase of the trial. These four equally spaced assessments over the 10 week study period will form the basis of a repeated measures analysis of variance in order to plot trajectories of pain as a function of treatment condition. We hypothesize a linear decrease in pain from baseline in the nVNS but not in the sham nVNS condition. Other variables (e.g., MIDAS, physical function part of the SF-36, CES-D) will be analyzed using the same general analytic approach; a simple *t*-test will be used to compare PGIC values between the groups at study end. We will define success criteria for PGIC and PF subscale of the SF-36 as scores of 5-7 and 0.5 SD improvement, respectively. Rate of drop out between the two groups while participating in the blinded phase of the trial will be tested for significance by Fisher’s test.

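### The Endpoints section lets baseline-to-end change count towards the primary objective, and nothing says that the between-arm ANCOVA alone decides

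*Combined protocol and SAP*

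**What the plan says.** Three places leave room for a within-arm claim.

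- Section 5e, Primary: "Assessment of this objective will be based on differences between active vs sham treatment data as well as between baseline and end of treatment data". This gives two bases and does not rank them; the second is the clause "as well as between baseline and end of treatment data".
- Section 1, Research Question: "The major research question is to determine if VNS reduces the widespread pain of GWI while sham VNS does not".
- Section 5h, Blinded study: "We will define success for this variable if it decreases by 30% or more over the course of the trial". The sentence names no comparator and does not say whether it applies to each patient or to an arm mean.

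Other places point to a comparison between arms.

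- Section 5h names the primary outcome: "Our primary outcome variable will be post-intervention pain severity in the treatment versus sham condition, controlling for pain severity prior to randomization".
- Section 5h then gives the analysis: "Post-intervention pain severity will be regressed on pre-intervention pain severity and intervention condition, using an analysis of covariance (ANCOVA) procedure".
- Section 4 bases the sample size on the effect of condition after adjustment for baseline pain, and the power paragraph in section 5h repeats that aim.
- Specific Aim 1 in section 1, and the opening sentence of the primary endpoint in section 5e, both set active against sham.
- All three secondary endpoints in section 5e compare change between the arms. Only the primary endpoint carries the additional baseline-to-end basis.

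The second analysis in section 5h is a repeated-measures ANOVA of pain trajectories by condition. Its hypothesis is worded arm by arm: "We hypothesize a linear decrease in pain from baseline in the nVNS but not in the sham nVNS condition". The condition-by-time interaction is not named as the test.

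**The concern.** Change from baseline in the active arm is not an effect of the device. It also contains placebo response, natural course and regression to the mean. Regression to the mean is likely here because entry requires a median of at least 5 over the five baseline ratings (sections 5b and 5f), and those same ratings supply the baseline score.

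The protocol recognises the problem. Section 2 says that the earlier uncontrolled results might have been non-specific and that the sham arm is there to settle this. Section 5f even withholds from participants that the device-use rule will not be enforced, so that sham users keep stimulating. If a baseline-to-end result can support the primary claim, that protection is lost at the point of interpretation. Section 24-week results are meant to support a proposal for a multi-site trial aimed at FDA approval (section 5d), so what may be concluded matters.

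**Working it through.** **Inputs**

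- From section 4: f² = 0.35, α = 0.05, power 0.80, stated total N = 26.
- From section 5c: 40 evaluable subjects, half per arm, so n = 20 per arm.
- Assumed: a standardised change δ (mean change divided by the SD of change) that is the same in both arms, so there is no device effect. The documents give no sham change, so δ runs from 0 to 1.0.
- Assumed, for the simulation only: normal scores with a pre-post correlation of 0.5.

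**The plan's own figure**

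Power is the probability that a noncentral F with 1 and N − 3 degrees of freedom and noncentrality λ = f²N exceeds the 5% critical value. There are two predictors, baseline and condition.

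- N = 25: λ = 0.35 × 25 = 8.75, power 0.807. This is the smallest N that reaches 0.80.
- N = 26: λ = 9.10, power 0.823.
- N = 40: λ = 14.0, power 0.954.

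Rounding 25 up to equal arms gives 26, so the stated figure is reproduced. It belongs to the test of the condition term. A joint test of both predictors would need 31.

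**Illustration of what a within-arm rule would do**

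All tests are two-sided at 0.05, with n = 20 per arm and no device effect.

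- Rule A, active arm significantly better than baseline: p = P(T′ > t₀.₉₇₅), where T′ is noncentral t with 19 df and noncentrality δ√20.
- Rule B, active arm significant and sham arm not: p(1 − p), because the arms are independent and share the same p. The maximum is 0.25, at p = 0.5.
- Rule C, the planned ANCOVA favouring active: 20,000 simulated trials at each δ.

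Example at δ = 0.5: noncentrality 0.5 × √20 = 2.24, p = 0.5645, and 0.5645 × 0.4355 = 0.246.

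| δ (assumed) | Rule A | Rule B | Rule C |
|---|---|---|---|
| 0 | 2.5% | 2.4% | 2.5% |
| 0.3 | 24.7% | 18.6% | 2.5% |
| 0.45 | 48.0% | 25.0% | 2.5% |
| 0.5 | 56.5% | 24.6% | 2.3% |
| 0.8 | 92.4% | 7.0% | 2.4% |
| 1.0 | 98.9% | 1.1% | 2.5% |

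**What the two bases in section 5e could mean together**

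From the same simulation:

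- If either basis sufficed, false success would be 4.3% at δ = 0, 56.6% at 0.5 and 98.9% at 1.0.
- If both were required, it follows by subtraction. At δ = 0 it is 2.54% + 2.40% − 4.31% = 0.6%. At δ = 0.5 it is 2.34% + 56.53% − 56.60% = 2.3%.

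So the harm depends on how the two bases combine, and the text does not say.

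**The case against.** The strongest reply is that the documents already name the deciding analysis. Section 5h labels the ANCOVA as primary, section 4 sizes the trial on it, and no within-arm significance test is specified for the blinded phase. The dependent-samples t-test in section 5h is confined to the open-label data. The closing clause of section 5e may simply name the two dimensions, arm and time, that a baseline-adjusted comparison uses. It could also mean that both conditions must be met, which would not inflate the error.

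Most of this stands. A reader might infer that the plan will judge success by separate tests in each arm, or that the research question and the trajectory hypothesis prescribe a comparison of two p-values. The documents do not support that. Section 1 states a question in plain language, and Aim 1 beside it is comparative. The trajectory sentence is an expected pattern attached to a secondary model that includes both arms.

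The reply does not remove the ambiguity. The clause lists a second basis that the secondary endpoints do without, no sentence ranks it below the ANCOVA, and the 30% success definition adds a criterion with no comparator.

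**Conclusion.** The point holds as an inconsistency over what may count as primary success. The primary analysis itself is sound: if the ANCOVA alone decides, false success in the device's favour is about 2.5% whatever the shared placebo response, and power at 40 evaluable is 0.954 for the planned f² = 0.35.

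The higher rates, up to 99% for Rule A and up to 25% for Rule B, should not be read as the trial's planned error rate. They describe rules that the plan does not adopt, at assumed values of δ. Rule B is also no worse than nominal at either end of the range. What the figures show is the cost of leaving a within-arm route open, and that is enough to justify closing it before the results are interpreted.

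**What to change.** 1. Section 5e: delete the clause "as well as between baseline and end of treatment data", or mark baseline-to-end change as descriptive.
2. Sections 5e and 5h: state that the ANCOVA-adjusted active-minus-sham difference in post-intervention pain, with its 95% CI, is the sole basis for the primary claim.
3. Section 5h: define the 30% criterion as a per-patient responder outcome and compare responder proportions between arms, in support of the ANCOVA. The earlier fibromyalgia results in section 2 were already counted per patient.
4. Section 5h: test the trajectory hypothesis by the condition-by-time interaction, and word it as a steeper decrease than sham.
5. Section 1: reword the question to ask whether VNS reduces pain more than sham.

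The cost is a few sentences. Sample size, data collected and procedures do not change.

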#### Secondary:

- Change in the Patient’s Global Impression of Change (PGIC) scale scores of overall symptom burden as completed by the subject from study onset to end of the blinded phase of the trial. Assessment of this endpoint will be based on a comparison between change occurring in active-treated versus sham-treated.
- Change in physical function subscale of the SF-36, a questionnaire assessing health related quality of life from study onset to end of the blinded phase of the trial. Assessment of this endpoint will be based on a comparison between change occurring in active-treated versus sham-treated.
- The difference between the active and sham treatment groups in change in number of migraine/headache days in the final week of the randomized/blinded period from the week prior to randomization.

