*Advantage and limitations of design:* The major advantage of the design in the FM study was that patients could enter the trial without having to stop their usual medical regimen. Since the widespread pain in these non-veterans is the same as that in veterans, moving the device to the treatment of veterans with WSP is a natural step. The design in the original study had two major limitations that we plan to rectify here: first, practicality of use – the stimulation electrodes and battery had to be surgically implanted by either a vascular surgeon or neurosurgeon, and the implantable system was expensive – costing more than \$30,000, including the costs of surgery; cost and need for surgical implantation greatly limited the practicality of using this treatment. Second, the design – the study had no sham-control limb, and so the dramatic therapeutic effects observed could have been non-specific responses to being in a therapeutic trial – i.e., placebo responding. Since [name] has never seen such a level of improvement either in his practice or in a recently completed double-blind placebo controlled trial of milnacipran in FM, he doubts the latter possibility. Nevertheless, the design we will present in this protocol will have a sham stimulation limb, and the trial itself will also be a double-blind study design. We expect that an important outcome of the study will be data to indicate that the positive results of the preliminary trial were directly due to vagus nerve stimulation and not due to a placebo effect.

To get around the cost issue, we have partnered in preparing this proposal with electroCore LLC (Basking Ridge, NJ), a biomedical device company that has developed a much less expensive hand-held, transcutaneous, non-invasive (nVNS) stimulator that eliminates the risks associated with surgery and can immediately be put to use as patients self-administer therapy. The device has recently received FDA approval for the acute treatment of pain associated with both cluster and migraine headaches. Importantly a recent study identified migraine in 64% of Gulf veterans with GWI. A secondary goal of this study will be to determine if Gulf veterans with WSP who also report having migraine will show improvement in their headache condition with nVNS when compared with sham nVNS treatment.

	Protocol Name:	Vagus Nerve Stimulation: A Non-Invasive Treatment to Improve the health of Gulf Veterans with Gulf War Illness

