## f) Procedures Involved in the Human Research

### Source data to be used in Study

*Numerical Rating Scale:* This is a zero to 10 visual analog scale asking veterans to rate the severity of their body-wide pain in the last 24 hrs where zero is no pain and 10 is worst pain possible.

*Kansas Criteria:* These criteria are followed in diagnosing Gulf War Illness. This is done via the history which collects medical information used to diagnose GWI through the endorsement of musculoskeletal pain at moderate or severe intensities. In addition to pain, veterans must endorse symptoms in at least 2 more of the following problem areas: Fatigue/sleep; cognitive and mood; Gastrointestinal; respiratory; skin.

*SF-36:* This is a 36 question vehicle used to assess a patient's health related quality of life. The version for veterans will be used. The physical function subscore will be one of the outcome measures

*Patient Global Assessment of Change:* This scale consists of 7 questions, each scored with a scale ranging from +3 [very much improved] through 0 [no change] to -3 [very much worse]

*Number of migraine days in the past week:* A migraine day is one where a patient has a headache lasting at least 4 hours

*Diary:* Patients will be required to complete a diary after they self administer each treatment to each side of his/her neck. The diary asks the time of the treatment and the stimulus intensity elected by the subject. After the final treatment for that day, the diary asks the patient if s/he has had a headache lasting at least 4 hours.

*Electronic Diary:* Patients will be required to complete a diary after they self administer each treatment to each side of his/her neck. The electronic diary asks the time of the treatment and the stimulus intensity elected by the subject. After the final treatment for the day, the diary asks the patient if s/he has had a headache lasting at least 4 hours. The electronic diary mirrors the paper diary, except that it is online with a secured web address. The subject can access with any electronic device with the capability of accessing the internet. A subject is given a unique 10 digit subject number to access the website. No other information is collected by the subject. Upon logging in for the first time, the subject creates a password and is the only person that can log into their eDiary. This is given as an option for subjects who prefer to use the electronic version over the paper version.

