**Blinded Phase of Study**

Encounter 6 – Office Visit [first time at ISMMS]: Confirmation of eligibility, randomization and device and diary training Visit. Subjects deemed eligible for study participation up to this point, will be invited to ISMMS in the Annenberg Building located at [name], within one week after Visit 5. They will sign consent for study participation. They will provide a fifth rating of widespread pain severity over the past 24 hours at this encounter on a 10-point VAS. The fifth pain rating will be added to the 4 VAS pain ratings done in the week after intake at the VA. If the median of all 5 VAS widespread pain ratings remains at least a 5, subjects remain eligible to participate. Then medical and eligibility information obtained on Encounters #1 through 5 will be briefly reviewed, a pregnancy test will be administered, and a medication history will be taken. If still deemed eligible to continue on in the study, they then complete questionnaires [MIDAS, SF-36 and HADS] and undergo a brief baseline medical evaluation consisting a physical examination including vital signs and a tender point examination and of asking the veteran questions to determine if s/he fulfill criteria for chronic fatigue syndrome, fibromyalgia, and/or irritable bowel syndrome and for Gulf War Illness. Subjects are then randomized and trained by the blinded trainer to use the device to which they have been assigned [devices are received with serial numbers covered and numbered sequentially so the trainer is blinded to condition]. Subjects will receive identical instruction and guidelines regardless of which device they receive. To be sure the subject knows how to use the device; s/he will be given a quiz about using the device after training. They will also be trained on use of a daily diary (paper and electronic) to be completed after each of the three daily treatments. Subjects will be given an unique 10 digit identifier that they will used to log into the Merge IBM site, in which they will be prompted to create a username and password.

Veterans will be reminded [as specified in the study consent form] that in order to proceed to the open label phase of the study, they must administer at least 70% of all programmed stimuli as well as complete at least 70% of the diary entries; however, because the device needs to be sent back to the

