	Protocol Name:	Vagus Nerve Stimulation: A Non-Invasive Treatment to Improve the health of Gulf Veterans with Gulf War Illness
	Principal Investigator:	[name]
	Primary Contact Name/Contact Info:	[name]: [contact]
	Date Revised:	07/15/2019
	Study Number:	HSM# 16-00097

manufacturer in order to obtain the stimulation data, resulting in a 3-4 day delay in retrieving the data, we will not be able to use this criterion to advance subjects to get an actual unit in the open label phase of the study. Therefore, although we will tell subjects they have to deliver at least 70% of all programmed stimuli in order to get an active unit, the only criterion that will be enforced is that they will have had to complete 70% of diary entries, which will be verified by reviewing their diary logs at Encounter #14. This procedure is in place so that veterans who do not perceive benefit from the treatment [i.e. those receiving sham stimulation] will continue to treat themselves per protocol; this is critical for the overall purpose of the study in order to be able to infer that it was the active treatment that produced the therapeutic effect. If subjects did not continue stimulating themselves, we would be unable to determine whether a placebo effect existed or not.

Encounter 7 – Phone Call: Within 7 ( $\pm 4$ ) days after Encounter 6 (Day 0), subject will receive a phone call from study personnel to inquire about any negative effects of stimulation (Adverse Events, AEs) and to check if they are using the diary after each stimulation.

Encounter 8 – Phone Call: Within 23 ( $\pm 4$ ) days after Encounter 6 (Day 0), subject will receive phone call from study personnel to inquire about AEs, check as to use of diary, rating of widespread pain over past 24 hours on a 10-point VAS, and potential desire to reduce medications.

Encounter 9 – Phone Call: Within 46 ( $\pm 4$ ) days after Encounter 6 (Day 0) subject will receive phone call from study personnel to inquire about AEs, check as to use of diary, rating of widespread pain over past 24 hours on a 10-point VAS, and potential desire to reduce medications.

Encounter 10 – Phone Call: Within 63 ( $\pm 4$ ) days after Encounter 6 (Day 0) subject will receive phone call from study personnel to inquire about AEs, check as to use of diary, rating of widespread pain over past 24 hours on a 10-point VAS, and potential desire to reduce medications.

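### The migraine-day endpoint uses one week after treatment although a daily headache item runs for 10 weeks; a last-28-day diary rate would be more precise using data already collected

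*Combined protocol and SAP*

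**What the plan says.** Section 5 e), Secondary, compares the arms on how a count of migraine or headache days changes between two single-week windows: "days in the final week of the randomized/blinded period from the week prior to randomization". Section 5 f), Source data, gives the definition: "A migraine day is one where a patient has a headache lasting at least 4 hours". The same list describes the diary: "After the final treatment for that day, the diary asks the patient if s/he has had a headache lasting at least 4 hours". Both the paper and the online form carry this question.

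Section 5 d) describes "the blinded phase of the study which will be 10 weeks in duration". The diary is introduced at Encounter 6, the randomization visit ("They will also be trained on use of a daily diary"), so it does not cover the week before randomization. Source data also lists the number of migraine days in the past week as an item of its own, apart from the two diaries.

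The Blinded study paragraph of Section 5 h) specifies ANCOVA on the baseline value for pain, and a repeated-measures analysis of pain over time. It says that other variables will follow the same general approach. Its examples do not include migraine days.

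**The concern.** Headache days are episodic. Seven days are a small sample of a patient's underlying rate, and subtracting one 7-day count from another carries the sampling noise of both weeks. The diary item uses the protocol's own 4-hour definition and runs for about 70 days per patient, yet the endpoint covers only the last 7 of them.

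Migraine is the second part of the research question in Section 1, and it concerns a subgroup only. Section 2 reports that "a recent study identified migraine in 64% of Gulf veterans with GWI", and Section 5 a) puts the share in the recruitment database at over half. Of 40 evaluable patients that is roughly 20 to 26 (0.50 × 40 = 20; 0.64 × 40 = 25.6), or 10-13 per arm. At that size, avoidable noise could leave a real effect unseen in a trial meant to inform a larger one.

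**Working it through.** **The plan's own figure.** The only sample-size calculation is for pain: f² = 0.35, alpha 0.05, power 0.80, total 26. A noncentral F test of one of two predictors gives 25 (power 0.807), and 26 gives 0.823, so the figure reproduces closely. It says nothing about migraine days, for which no power is stated.

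**Inputs from the documents.** Post-treatment window 7 days; blinded diary 70 days; baseline one week; 1:1 allocation.

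**Assumptions (not in the documents).** Each patient has a stable daily headache probability. The mean is m = 1.05, 2.1 or 3.15 days per week, the between-patient SD of the weekly rate is s = 0.7 or 1.4, and all diary days are answered.

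**Formulas.** With μ = m/7, the mean within-patient daily variance is E = μ(1 − μ) − (s/7)². A weekly rate from D days has variance V_D = s² + 49E/D, and its covariance with the baseline week is s². After adjustment for the baseline week, the residual variance is R_D = V_D − s⁴/V_7.

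**Example, m = 2.1, s = 1.4.** E = 0.21 − 0.04 = 0.17. V_7 = 1.96 + 1.19 = 3.15. s⁴/V_7 = 3.8416/3.15 = 1.22. R_7 = 3.15 − 1.22 = 1.93. R_28 = 1.96 + 0.30 − 1.22 = 1.04. Ratio 0.54; SE ratio √0.54 = 0.73.

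**Linear build-up.** If the effect is proportional to the day number, days 43-70 average 56.5 and days 64-70 average 67, so the 28-day window captures 56.5/67 = 0.84 of the final-week effect. The relative signal-to-noise is 0.84/√(R_28/R_7).

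| m | s | E | R_7 | R_28 | Ratio | SE lower by | Signal-to-noise gain, linear effect |
|---|---|---|---|---|---|---|---|
| 1.05 | 0.7 | 0.1175 | 1.13 | 0.51 | 0.45 | 33% | 25% |
| 1.05 | 1.4 | 0.0875 | 1.08 | 0.62 | 0.57 | 24% | 11% |
| 2.1 | 0.7 | 0.2000 | 1.76 | 0.71 | 0.40 | 36% | 33% |
| 2.1 | 1.4 | 0.1700 | 1.93 | 1.04 | 0.54 | 27% | 15% |
| 3.15 | 0.7 | 0.2375 | 2.04 | 0.79 | 0.39 | 38% | 35% |
| 3.15 | 1.4 | 0.2075 | 2.29 | 1.20 | 0.52 | 28% | 17% |

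**Stronger within-patient correlation.** Write the daily variance as 1 and the correlation between any two days of one patient as ρ. Then V_D = ρ + (1 − ρ)/D and R_D = V_D − ρ²/V_7. At ρ = 0.5, R_7 = 0.571 − 0.438 = 0.134 and R_28 = 0.518 − 0.438 = 0.080; the ratio is 0.60 and the linear-effect gain 9%. At ρ = 0.6 the ratio is 0.61 and the gain 8%.

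**Share of information, and power.** Assume instead a mean of 2-3 days per week, ρ of 0.1-0.5, 70-100% of diary days answered, a true final difference of 1 day per week, and 10-13 patients per arm. With baseline adjustment, the final week carries 31-52% of the information in the 10 weeks if the effect is constant, 47-50% if it is linear, and 32-38% if it plateaus at week 4. Power by ANCOVA:

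| Post-treatment value | Constant effect | Linear effect |
|---|---|---|
| Final week | 0.26-0.60 | 0.26-0.60 |
| Last 4 weeks | 0.48-0.81 | 0.37-0.68 |
| Unweighted 10-week mean | 0.58-0.87 | 0.22-0.39 |

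A plain 10-week mean can therefore do worse than the final week. A late window improves on the final week in both cases. The normal approximation is slightly optimistic at these sizes.

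**The case against.** The strongest defence is that an end-of-treatment week is a coherent target. It matches the primary pain endpoint, which also uses the last blinded week, and it keeps one-week windows at both times. The endpoint is secondary, in a small proof-of-principle trial, and no bias is shown. All of that stands; the point is about efficiency.

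The baseline week also precedes the diary. Lengthening only the post-treatment window cannot remove baseline noise, and a diary rate minus a baseline count from another source would not compare like with like. That rules out a change score. It does not bias a randomized comparison of post-treatment rates that uses the baseline only as a covariate.

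Three stronger readings are tempting, and the documents do not support them:

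- A reader might infer that the plan commits to an unadjusted change score. The catch-all sentence in Section 5 h) may already imply ANCOVA, since its list of variables is only illustrative.
- A reader might infer from "the only criterion that will be enforced is that they will have had to complete 70% of diary entries" that a compliant patient has about 5 answered days in the final week (0.7 × 7 = 4.9) and that blank days count as headache-free. That rule covers entries over the whole blinded phase and controls entry to the open-label phase; it sets no level for any one week. The separate past-week item means the count may not come from the diary at all, and no passage says how blanks are treated.
- A reader might infer that 90% of the information is lost because 63 of 70 days are unused. Days within a patient are correlated and the baseline stays noisy, so the loss is nearer half to two thirds. MIDAS also covers 2.5 months, although it measures disability by recall.

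**Conclusion.** The point holds as a low-cost improvement to a secondary endpoint. On the assumed headache rates, a last-28-day window has 39-57% of the residual variance of the final week (SE about 24-38% lower). If benefit builds linearly, the net signal-to-noise gain is about 8-35%; the lower end comes from strong within-patient correlation. Headache bouts lasting several weeks would shrink it further. Every rate, SD and correlation here is an assumption.

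It would go too far to say that the one-week window by itself makes the migraine comparison fail. With 10-13 patients per arm, power stays modest under a linear effect even with the 28-day window. The primary pain analysis is not touched.

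**What to change.** 1. In Section 5 e), define the post-treatment value as headache days per week over the last 28 days of the blinded phase, from the diary: headache days divided by diary days answered, times 7. This leaves unanswered days out and assumes that they resemble the answered ones.
2. In Section 5 h), name this endpoint and state that the ANCOVA approach applies to it, with the baseline-week count as covariate.
3. State where the baseline-week count comes from, given that the diary starts at Encounter 6. Use it only as a covariate, and form no diary-minus-baseline change score.
4. Keep the final-week count as a supportive analysis, and state whether it comes from the diary or from the past-week item.

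The cost is a wording amendment with no new data collection. Section 10 refers to subjects who have already taken part, so the change should be made and dated before anyone sees headache results by arm. The downside is slight attenuation if benefit is still building in weeks 7-9: about 16% under a linear course (1 − 0.84). Baseline noise remains.
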